6.5.3.4 Management of Acute "in Radiation Field" Toxicity

If dermatitis, mucositis, or dysphagia occurs, the possibility of IMRT interruption should be assessed according to their severity. Institutional guidelines on prophylaxis and dental hygiene will be followed for management of skin and mucosal toxicity.

For any other degree of minor toxicity, the necessary support measures must be taken to ensure treatment continuity ([Peterson 2015](#)).

In the event of mucositis, the following recommendations will be considered:

- Rapid escalation of analgesics using the World Health Organization cancer pain relief ladder ([WHO 2018](#)).
- Enteral or parenteral nutritional support according to the institutional guideline. Enteral nutritional support is strongly recommended if weight loss is $\geq 5\%$. If the weight loss is $\geq 10\%$, the use of a nasogastric or gastrostomy tube must be implemented as quickly as possible ([Elad 2019](#)) and access to adequate nutritional support needs to be secured by the Investigator.

The management of radiation dermatitis should be based on the severity of symptoms, as determined by Radiation Therapy Oncology Group and should follow the recommendations by the Supportive Care Guidelines Group.

6.5.3.5 **End of Radiotherapy**

Radiotherapy will be administered until completion of the IMRT dose and schedule (see [Table 9](#)) planned in the study or until any of the study intervention discontinuation criteria described in Section [7.1](#) occur.

Note: Radiotherapy discontinuation will not result in xevinapant discontinuation or chemotherapy discontinuation. See further Section [6.5.1.3](#).

Treatment interruption and permanent discontinuation of any of the components of the study intervention is to be recorded in the Dosing CRF of each component of the study intervention. For each action, the reason must be recorded.

Discontinuation from study intervention does not mean discontinuation from the study. Procedures to be followed in the event of a study intervention discontinuation are presented in Section [7.1](#).

Procedures for discontinuation from study (not only study intervention) are described in Section [7.2](#).

6.6 **Continued Access to Study Intervention After the End of the Study**

Not applicable

6.7 **Treatment of Overdose**

For this study, any dose of xevinapant greater than **CCI** mg/day and/or xevinapant intake exceeding 14 days per cycle, any dose of cisplatin higher than **CCI** mg/m² per cycle, or any dose of carboplatin higher than AUC **CCI** per cycle, will be considered an overdose.

The Sponsor has no specific recommendation for treating an overdose. The Investigator will use their clinical judgment to manage any overdose, considering the symptoms, and any site procedures or standards. Appropriate supportive treatment should be provided if clinically indicated. In the event of overdose, the participant should be observed closely for signs of toxicity.

Even if not associated with an AE or SAE, any overdose is recorded in the CRF and reported to global patient safety in an expedited manner. Overdoses are reported on an SAE and Overdose Report Form, following the procedure in [Appendix 7](#).

6.8 **Concomitant Therapy**

Record in the CRF all concomitant therapies (e.g. medicines or nondrug interventions) used from the signing of the ICF until the EOS visit at the timepoints specified in the SoA (Section [1.3](#)), including any changes. For prescription and over-the-counter medicines, vaccines, vitamins, and

herbal supplements, record the name, reason for use, dates administered, and dosing information. For nondrug interventions, record the name, and dates administered.

Contact the Medical Monitor for any questions on concomitant or prior therapy.

6.8.1 Permitted Medicines

Permitted medicines are the following:

- Medication to prevent or treat concomitant diseases or to treat adverse effects of investigational intervention are allowed unless otherwise specified in the sections below.
- Any medicines that are considered necessary to protect the participant's welfare in emergencies may be given at the Investigator's discretion, regardless of if it results in a protocol deviation.
- Investigators will assess prior to, or at the beginning of the screening period, whether a participant will be vaccinated against a specific infectious disease (e.g. COVID-19 or mpox infection) that may be a significant risk to the participant during the study before receiving the first dose of study intervention.

In general, Investigators will consider that the vaccination effect may be reduced in participants with cancer and may not lead to protection depending on the extent of the immunocompromised state of the participant, including the impact of prior therapies.

6.8.1.1 Antiemetics

The specific antiemetic regimen is at the discretion of the Investigator, provided adequate control is achieved. Related information should be reported in the eCRF. For participant receiving cisplatin, antiemetic therapy including dexamethasone (or any other corticosteroid at equivalent dose iv.), 5-HT3 serotonin receptor antagonists and neurokinin-1 receptor antagonists can be administered as per 2016 MASCC and ESMO guideline ([Roila 2016](#)). However, dosage/schedule adjustment for both the dexamethasone and aprepitant should be considered, due to elevated plasma concentrations of these drugs fold triggered by xevinapant inhibition of CYP3A4. Strong CYP3A4 inhibitors increased AUC of dexamethasone ~ 3-4 fold and AUC of aprepitant ~ 5 fold, respectively.

For instance, the Investigator can consider the following regimen:

Day of cisplatin administration (Day 1 of cisplatin = Day 2 of each treatment cycle):

- 5-HT3 serotonin receptor antagonists iv., at the appropriate antiemetic dose for highly emetogenic regimens. If ondansetron is used with xevinapant, participant should be monitored closely (see also Section [6.5.2](#)). Alternative 5-HT3 serotonin receptor antagonists should be used, if possible.
- Dexamethasone: 8 mg or any other corticosteroid at an equivalent dose orally (to be taken 30 minutes prior to chemotherapy).

- Aprepitant: oral 125 mg at least 30 minutes prior to infusion.

Day 2 after cisplatin administration: Dexamethasone 4 mg + aprepitant 80 mg/day ± 5-HT3 serotonin receptor antagonist

Day 3 after cisplatin administration: Dexamethasone 4 mg ± 5-HT3 serotonin receptor antagonist

For participants receiving carboplatin, antiemetic therapy including dexamethasone (or any other corticosteroid at an equivalent dose iv.) and 5-HT3 serotonin receptor antagonists may be administered as per 2016 MASCC and ESMO guideline ([Roila 2016](#)). If dexamethasone is used, the modified dosage/schedule described above for cisplatin could also be considered.

Note: Dose and schedule of dexamethasone coupled with its wide availability in various forms established it as the agent of choice in the 2016 MASCC and ESMO guidelines. If an equivalent dose of corticosteroids is used according to institutional guidelines, the risk of increased toxicity to corticosteroids should be carefully monitored. Elevations of plasma levels may be triggered by xevinapant inhibition of CYP3A4 as described above for dexamethasone.

The metabolism and transport of the above listed drugs occurs through CYP3A4/5 and/or P-gp. As per their product information, the clinical relevance of their coadministration with inhibitors or inducers of such enzymes and transporters is difficult to anticipate. In view of the in vitro DDI profile of xevipitant, the activity, and risk of toxicity of these drugs may be increased when coadministered with xevipitant.

Gastric Mucosal Protectants

Gastric mucosal protectants, if needed, cannot be taken within 2 hours before or 2 hours after xevinapant intake because their concomitant intake may decrease the absorption of xevinapant. Participants must be instructed accordingly.

6.8.3 Prohibited Medicines

6.8.3.1 Prohibited Medications with Xevinapant

- Participants are prohibited from receiving the following therapies during the screening and treatment phases: anticancer systemic chemotherapy, anticancer immunotherapy, or anticancer biological therapy not specified in this protocol.
- Use within 14 days prior to study intervention start or requirement for ongoing treatment with any drug(s) on the prohibited medication list in Sections [6.8.3.1.1](#), [6.8.3.1.2](#), [6.8.3.1.3](#), and [6.8.3.1.5](#) or within 3 days prior to study intervention start for the drugs in Section [6.8.3.1.4](#) is an exclusion criterion.

- Treatment with an investigational agent other than xevinapant or use of an investigational device within 4 weeks of the first dose of study intervention or during study intervention.
- In case of unavoidable concomitant administration of a prohibited medicine during investigational treatment, the need for suspension or discontinuation of xevinapant must be discussed beforehand with the Sponsor.
- Live vaccines within 28 days prior to the start of study intervention and up to 90 days after EOT are prohibited. Examples of live vaccines include, but are not limited to, the following: measles, mumps, rubella, chicken pox, yellow fever, rabies, bacille Calmette-Guerin, and typhoid (oral) vaccine. Seasonal influenza vaccines for injection are generally killed virus vaccines and are allowed; however, intranasal influenza vaccines (e.g. Flu-Mist®) are live attenuated vaccines and are not allowed.
- The use of hematopoietic growth factors is prohibited during the concomitant RT phase of the study.
- Other preparations and medications such as those listed in the below sections are strictly prohibited in combination with xevinapant.

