18F-FDG-PET=[¹⁸F]Fluorodeoxyglucose, 3QM=Every 3 months, AESI=adverse events of special interest, CT=computed tomography, ECOG PS=Eastern Cooperative Oncology Group Performance Status, EOS=End of Study, EOT=End of Treatment, FU=Follow-up, MRI=magnetic resonance imaging, PD=progressive disease, SAE=serious adverse event

Figure 3 Treatment Diagram and Time Window for Visits

C=cycle, D=day, EOT=end of treatment, IMRT=intensity-modulated radiation therapy, QW= once a week, W=week.

- On days when IMRT is to be administered, xevinapant must be administered before IMRT.
- During the treatment period, each study visit day and allowed time windows will be based on the C1D1 date. C1D1 and C1D2 are triggered by the first administration of xevinapant and QW cisplatin, respectively. These visits should be performed on consecutive days. Crossed gray boxes in the row "Time Window for Visit" represent days around a specific study visit (represented by solid black boxes in the row "Study visit day") where the visit can be rescheduled (see also time windows planned in the SoA, [Table 1](#), [Table 2](#), and, [Table 3](#)).
- Xevinapant once daily from D1 to D14 of each cycle (solid red boxes) [CCI](#)
- Cisplatin-based chemotherapy weekly on C1D2, C1D9, C1D16, C2D2, C2D9, C2D16, and C3D2 (see also Section [6.5.2](#)). For participants not eligible to continue with QW cisplatin after dose reduction switch to carboplatin at the next scheduled chemotherapy administration.
- IMRT should be delivered in 35 fractions over 7 weeks, 5 fractions weekly (solid yellow boxes). If IMRT is put on hold due to safety or administrative reason, the 7 weeks of IMRT can be administered until Study Week 9 (dotted yellow boxes) (also see Section [6.5.3](#)).
- The EOT visit will be performed 14 days (\pm 7 days) after last study intervention administration (i.e. xevinapant, chemotherapy, or IMRT whichever is administered last) or 14 days (\pm 7 days) after premature discontinuation during treatment, but prior to start of any subsequent anticancer therapy.

Table 4

Schedule of Activities: Pharmacokinetic Assessments

Treatment Day	Timepoint	Xevinapant PK Sampling
C1D2	Predose xevinapant (window: less than 1 hour prior to dosing)	X
C1D2	End of cisplatin infusion (window: less than 30 min after end of infusion)	X
C1D9	Predose xevinapant (window: less than 1 hour prior to dosing)	X
C1D9	1-2 hours after end of cisplatin infusion	X

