6.5.3.2 Treatment

Full details of radiotherapy protocol requirements including volumes, OAR, and OAR dose constraints can be found in the RT Manual provided for this study. A QA procedure will be applied for this study. The RT-QA Review Center (Appendix 5) will centrally review the IMRT treatment plan(s) including other treatment-related information submitted by the Investigator to ensure compliance with protocol guidelines and provide feedback to the site (refer to the RT Manual). The IMRT plan must be reviewed by the RT-QA Review Center prior to the start of the IMRT. A summary of radiotherapy requirements and recommendations is described below.

CCI

A matched conventional anterior neck field is not permitted. During treatment, daily image-guided radiation therapy (IGRT) is required with either kV or MV guidance.

For CT simulation, the participant must be in a supine position and immobilized with a thermoplastic (or similar) mask that includes the head and neck with strong consideration of the shoulders as well. Intraoral immobilization devices are at the discretion of the Investigator. A slice thickness of 3 mm or less is required and the field of view must extend from the top of skull to the bottom of the carina. Intravenous contrast is recommended at the time of simulation.

Standard fractionation IMRT (as fully described in the IMRT manual) is to be started on C1D1 after administration of xevinapant (see administration schedule in [Table 2](#)). On days where all treatment components should be administered, IMRT should be preferably administered after xevinapant and chemotherapy.

IMRT will be delivered per [Table 9](#) and the following:

- To the PTV and high-risk clinical target volume: 70 Gy in 35 fractions over 7 weeks, 2.0 Gy/fraction, 5 days/week. Missed treatments due to holidays or logistic reasons can be compensated by delivering the missed fraction before or after the end of the combination treatment period (i.e. up to Week 9 after administration of first dose) (see Section [6.5.3.3](#)).
- Elective irradiation (low risk) to locoregional areas, 56 Gy (1.6 Gy/fraction per day, 5 fractions per week [5/7 days]).

Table 9 **Radiation Therapy Scheme**

	Total dose in Gy	Dose in Gy	Number of days	
PTV 70	70	2	35	5 fractions per week over 7 weeks
PTV 56	56	1.6	35	5 fractions per week over 7 weeks

PTV=Planning target volume.

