6.8.3.1.1 Recombinant Human Erythropoietin and Derivates

Recombinant human erythropoietin (EPO) is not allowed throughout the entire duration of the study.

Preclinical and clinical studies showed that autocrine or paracrine erythropoietin signaling can enhance cancer invasion in SCCHN and negatively affects patient outcome in terms of OS and local-regional PFS ([Henke 2003](#), [Lambin 2009](#)).

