6.8.3.1.5 Prohibited or Concomitant Use of Traditional Chinese Medicines

Any traditional Chinese medication with approval for use as anticancer treatment (regardless of the type of cancer) will not be permitted during study intervention. Traditional Chinese medicines for indications other than anticancer treatment, such as supportive care, may be administered at the discretion of the Investigator. Any traditional Chinese medicines or herbal supplement, if known to be strong inhibitors/inducers of CYP3A4 or inhibitors of P-gp, will not be permitted. Use of traditional Chinese medicines as part of next line of anticancer treatment should be documented as such.

6.8.3.2 Prohibited Medications and Medications to be Used with Caution with Cisplatin or Carboplatin

Prohibited medications

Platinum-based cytotoxic agents may reduce the digestive absorption of phenytoin and fosphenytoin, resulting in reduced epilepsy control and risk of exacerbation of convulsions. Therefore, both phenytoin, and fosphenytoin are prohibited during the combination therapy period.

Granulocyte-Colony Stimulating Factors (G-CSF) are not allowed throughout the screening period and for prophylaxis. Nevertheless, for participants presenting with febrile neutropenia who have

risk factors for infection-related complications or poor clinical outcome, therapeutic G-CSF including secondary prophylaxis should be considered (Becker 2020). Features associated with poor outcome include age > 65 years; sepsis syndrome; ANC < 100 neutrophils/m³; anticipated prolonged (> 10 days) neutropenia, pneumonia, or other clinically documented infection; invasive fungal infections; and hospitalization at the time of fever.

Please also refer to the local product information for cisplatin or carboplatin, as applicable.

Medications to be used with caution

Please consult and follow the instructions provided in your local label.

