## 10.2 Protocol Deviations / Exclusion from Analysis Sets

### 10.2.1 Important Protocol Deviations

Important protocol deviations (IPDs) are protocol deviations that might significantly affect the completeness, accuracy, and/or reliability of the study data or that might significantly affect a participant's rights, safety, or well-being.

Important protocol deviations include:

- Participants enrolled and dosed on the study who did not satisfy enrolment criteria
- Participants that develop withdrawal criteria whilst on the study but are not withdrawn
- Participants that receive the wrong study intervention or an incorrect dose
- Participants that receive an excluded concomitant medication
- Failure to collect data necessary to interpret primary endpoints
- Failure to collect necessary key safety data
- Deviation from Good Clinical Practice (GCP)
- Any other protocol deviation that might significantly affect the completeness, accuracy, and/or reliability of the study data or that might significantly affect a participant's rights, safety, or well-being.

Important protocol deviations will be identified for all participants by either site monitoring, medical review processes or programming and confirmed prior to or at the Data Review Meeting at the latest.

Any protocol deviation is documented in SDTM datasets whether identified through site monitoring, medical review or programming. The management of protocol deviations is outside of this IAP document.

Important protocol deviations or important events that might have an effect on PK include, but may not be limited to the following:

- Sample processing errors that may lead to inaccurate bioanalytical results
- Inaccurate dosing or dosing errors (e.g., dose administration delayed, dose change or missed doses), when dosing information is available
- Pre-dose or trough sample collected after the actual dosing
- Concomitant medications and dietary or herbal supplements that are known potent inhibitors or inducers of P-glycoprotein (Table 13 of protocol).

Should one or more of these events be available at the Data Review Meeting, its implication for PK evaluation will be discussed and agreed amongst relevant study team members (e.g. Sponsor Clinical Pharmacology/Biostatistics/Clinical Pharmacokinetics & Pharmacodynamics team representative). Appropriate action will be taken such as flagging individual values to be excluded from analysis.

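### Protocol 6.8.3.1 bans all growth factors during radiotherapy, while 6.8.3.2 recommends considering G-CSF for high-risk febrile neutropenia, and no visible text says which rule prevails

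*Protocol*

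**What the plan says.** Three provisions of the Protocol deal with growth factors.

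- Section 6.8.3.1 (prohibited with xevinapant): "The use of hematopoietic growth factors is prohibited during the concomitant RT phase of the study". The bullet has no exception and no cross-reference.
- Section 6.8.3.1.1: "Recombinant human erythropoietin (EPO) is not allowed throughout the entire duration of the study".
- Section 6.8.3.2 (with cisplatin or carboplatin): G-CSF is barred during screening and as prophylaxis. For febrile neutropenia with risk factors for infectious complications or poor outcome, however, "therapeutic G-CSF including secondary prophylaxis should be considered". The RT phase is not mentioned.

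Two further provisions set the consequences. If a prohibited medicine is unavoidable, Section 6.8.3.1 requires that "the need for suspension or discontinuation of xevinapant must be discussed beforehand with the Sponsor". SAP 10.2.1 lists as an important protocol deviation: "Participants that receive an excluded concomitant medication". SAP 7.1 keeps a protocol deviation listing in the reduced, synoptic report.

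**The concern.** The two sections give opposite instructions on the same drug in the same treatment phase. An investigator who follows 6.8.3.2 may be giving a prohibited medicine, with the Sponsor discussion and deviation status that this brings. One who follows 6.8.3.1 withholds a treatment that 6.8.3.2 says should be considered for participants such as those with sepsis or an ANC below 100. Two sites could act differently and each cite the protocol, and identical use could be listed as a deviation or not.

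The situation is foreseeable. Section 6.5.2.1 expects myelosuppression. Appendix 3 puts it at 25% to 30% of cisplatin-treated patients and mentions fever and infection in those with neutropenia. Section 8.2.5.1 makes Grade 3 or higher febrile neutropenia a DLT-like event.

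**Working it through.** The plan states no figure on this point. The check has two parts: do the rules apply at the same time, and does any other text settle the conflict?

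**Inputs**

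- Cisplatin days (Section 1.3, notes to Figure 3): "Cisplatin-based chemotherapy weekly on C1D2, C1D9, C1D16, C2D2, C2D9, C2D16, and C3D2", with 21-day cycles.
- RT start (Section 6.5.3.2): standard-fractionation IMRT "is to be started on C1D1 after administration of xevinapant".
- RT length (Section 6.5.3.2): 35 fractions, 5 per week, over 7 weeks.

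**Cisplatin study days.** Study day = 21 × (cycle − 1) + cycle day.

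- Cycle 1: Days 2, 9, 16
- Cycle 2: 21 + 2, 21 + 9, 21 + 16 = Days 23, 30, 37
- Cycle 3: 42 + 2 = Day 44

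**Last planned RT fraction** (weekday treatment, no interruptions)

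- Day 1 a Monday: seven full weeks, ending on the Friday of week 7, 1 + 6 × 7 + 4 = Day 47.
- Day 1 a Tuesday: 4 fractions in the first calendar week plus 6 × 5 = 30 gives 34. The 35th falls on the next Monday, Day 49.
- Day 1 a Wednesday, Thursday or Friday: the same count also ends on Day 49.

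**Overlap**

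| Quantity | Result |
|---|---|
| Planned cisplatin doses on or before the last fraction | 7 of 7 |
| Doses 2 to 7, the only ones secondary prophylaxis could cover (Days 9 to 44) | 6 of 6 inside RT |
| Seventh dose to last fraction | 47 − 44 = 3 to 49 − 44 = 5 days |
| Earliest onset of febrile neutropenia outside the ban | Day 48 to 50, which is 4 to 6 days after dose 7 |

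On the planned schedule the ban removes every use of the secondary prophylaxis that 6.8.3.2 allows. It also covers therapeutic use for any episode that begins by Day 47 to 49.

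**Can other text settle it?**

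- *Does the ban mean erythropoietin only?* Erythropoietin is already barred for the whole study by 6.8.3.1.1, so on that reading the RT-phase bullet would add nothing. In ordinary use, hematopoietic growth factors include G-CSF.
- *Does the exception in 6.8.3.2 override the ban?* It qualifies the sentence just before it, on screening and prophylaxis. It does not refer to 6.8.3.1.
- *Does the emergency clause (Section 6.8.1) help?* It lets the investigator give needed medicines in an emergency "regardless of if it results in a protocol deviation". Deviation status stays open, and planned prophylaxis before a later dose is not an emergency.
- *Does the conflict rule in Section 6.5.1.2 help?* It covers conflicting dose adjustments, not concomitant medicines.

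**The case against.** The strongest reply is that 6.8.3.2 is the only visible rule that names G-CSF. Since the ban would leave its secondary-prophylaxis wording without any use on schedule, the authors probably meant the specific exception to govern, and only a cross-reference is missing. This is a reasonable guess at intent, but the protocol does not say it. The ban is the more specific rule on timing, so the argument can be turned round.

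Other points on that side:

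- **Medical Monitor.** Section 6.8 directs questions on concomitant therapy to the Medical Monitor. That is a route to an answer, not a rule, and does not guarantee the same answer each time.
- **Repetition.** The protocol repeats itself elsewhere (St John's wort, dronedarone), so the separate erythropoietin ban does not prove what the RT-phase bullet was meant to add. This weakens that one inference. The ordinary meaning of the term still includes G-CSF.
- **Redaction.** Tables 7 and 8 may address neutropenia management. This stands as a limit: the finding concerns the visible text.
- **Deviation handling.** The prohibited medication list cited in 6.8.3.1 points to subsections that do not name G-CSF. SAP 10.2.1 has important deviations confirmed by the Data Review Meeting and places their management outside the SAP. Classification as a deviation is therefore possible, not certain, and that uncertainty is the problem.
- **Small effect now.** SAP version 2.0 (14 March 2025) reduces the study to a first safety committee analysis with 6 patients and a synoptic report based on a 20 September 2024 database lock. This also stands: new wording may have little prospective effect on this study's conduct.

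**Conclusion.** The concern holds: Sections 6.8.3.1 and 6.8.3.2 contradict each other as written. The overlap is complete on the planned schedule, with 7 of 7 cisplatin doses, and 6 of 6 doses open to secondary prophylaxis, inside the RT phase.

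This assumes RT starts on C1D1, fractions are given on weekdays and nothing is interrupted. Febrile neutropenia that starts after RT has ended is outside the conflict. So are chemotherapy doses given after RT because of a delay or early RT discontinuation. How many participants are affected cannot be estimated. The consequence lies in patient management and consistent deviation reporting; nothing here bears on the sample size.

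**What to change.** Add an exception to the 6.8.3.1 bullet for therapeutic G-CSF in febrile neutropenia as specified in Section 6.8.3.2, and state there whether secondary prophylaxis is allowed during RT. Classify all G-CSF use in the deviation listing by that single rule.

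If the clinical team intends the ban to prevail, limit the 6.8.3.2 exception to the period after RT and delete its secondary-prophylaxis wording, because no planned cisplatin dose remains by then.

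Either choice costs protocol wording and one classification rule, with no added visits or data. Given the reduced scope in SAP 7.1, the classification rule matters most for this study's report. The wording correction matters most wherever this protocol text is reused.
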